###### 4.4.2.1.1. Analysis for CGM Parameters

The time in glucose ranges will be based on the percentage of CGM readings within the glucose ranges, and glucose variability will be based on the readings during the specific CGM session. Section 6.6 (Appendix 6) provides the derivation of CGM parameters.

Longitudinal logistic regression model with treatment, strata (country, routine use of personal CGM or FGM at randomization and baseline HbA1c stratum ( $<8.0\%$  and  $\geq 8.0\%$ )), time, and treatment-by-time interaction as fixed effects, baseline value as a covariate will be used for analysis for CGM targets of glycemic control. See Section 4.3.2 for variance-covariance structure selection.

Time in glucose range between 70 and 180 mg/dL (3.9 and 10.0 mmol/L) inclusive collected during the CGM session that occurs between Week 22 and Week 26 is not a key secondary endpoint. To be consistent with other studies in the same program, this CGM parameter will also be analyzed using an ANCOVA model for treatment regimen estimand similar to that for the primary endpoint. The missing data will be imputed by multiple imputation with the approach similar to the imputation used for the primary endpoint.

The time point for primary CGM data analysis is CGM session. In addition, the average time in glucose range, hypoglycemia range and hyperglycemia range by week (by visit for treatment period) will be summarized by treatment. Average daily time since last dose by CGM Session during treatment period will also be summarized for LY3209590. Missing data patterns will be summarized at daily, weekly (visit) and CGM session levels.

#### **4.4.2.1.2. Study Insulin Dose Analysis**

For study basal insulin dose, both average daily and weekly dose during each visit for individual participants will be analyzed. In the LY3209590 group, the average weekly dose of each visit (that is, average of weekly doses since last visit) will be used as the average weekly dose, and the average daily dose will be the average weekly dose divided by 7. For insulin glargine group, the average daily dose since last visit will be computed for each visit, and the average weekly dose will be calculated as average daily dose  $\times$  7. For participants using typical once-daily pre-study basal insulin, the average pre-study basal dose during the screening/lead-in period will be the corresponding baseline daily dose. For participants using pre-study U-300 or Neutral Protamine Hagedorn twice daily (NPH BID), the average pre-study basal dose during the lead-in period multiplying by 0.8 will be the baseline daily dose. The baseline daily dose multiplying by 7 will be the baseline weekly basal insulin dose. The corrected baseline basal insulin dose will be controlled in the model for the insulin dosing analysis.

The daily prandial insulin dose will be calculated as the sum of the prandial insulin doses for morning meal, midday meal, evening meal, and additional dose of the day. All data including 0 dose and single dose of a day are included for analysis. On the first day of study treatment, a participant may have used both pre-study prandial insulin and study provided insulin lispro. Therefore, Week 0 (first day of study treatment) will be excluded from calculating the average daily prandial insulin for baseline and post-baseline period. The weekly prandial insulin dose at each visit is the average daily prandial insulin dose at the same visit  $\times$  7.

The weekly total insulin dose is the sum of average weekly basal insulin dose and average weekly prandial insulin dose. The daily total insulin dose is weekly total insulin dose divided by 7.

The basal/total insulin dose ratio at each visit is the ratio of average weekly basal insulin dose and average weekly total insulin dose at the same visit.

If either weekly basal insulin dose or weekly prandial insulin dose is missing, the total weekly insulin dose and basal/total insulin dose ratio will be set as missing for analysis. Similarly, the total daily insulin dose is also set as missing.

The analysis will be done for

- both daily dose and weekly dose in U for each of the basal, prandial and total insulin, respectively.
- dose in U/kg/day for basal, prandial and total insulin, respectively
- basal/total insulin dose ratio

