Diabetes Injection Device Experience Questionnaire (DID-EQ)																										X	X		Collected on paper form.		
Laboratory Tests and Sample Collections																															
Hematology	X		X													X										X	X		X		
Hemoglobin A1c (HbA1c)	X		X		X		X									X	X								X	X		X			
Clinical chemistry	X		X													X										X	X		X		
Glucose								X																							
Lipid panel				X																						X	X		X		

	Screening and Lead-In		Treatment																						Safety Follow-up				
			1	2	3	4	5	6	7	8	9	10	11	12	13	14	15	16	17	18	19	20	21	22	23	ED	UV		
Visit Number																											V801	V802	V1 = Screening V2 = Lead-In ED: Early Discontinuation UV: Unscheduled Visit V801, V802: Safety Follow-up
Weeks from Randomization	-3	-2	0	1	2	3	4	5	6	7	8	9	10	11	12	14	16	18	20	22	24	25	26	—		29	31		
Visit Interval Tolerance (days)		±3	—	±3	±3	±3	±3	±3	±3	±3	±3	±3	±3	±3	±3	±3	±3	±3	±3	±3	±3	±3	±3	±3	—		+7	±7	
Visit Detail			F		T	F	T		T	T	T	F	T		T	T		T	T	F	F			T	F	T = telehealth visit; F = fasting visit			
Urinalysis	X																											X	
Serum pregnancy	X		X																										Collect for WOCBP only.
Urine pregnancy (local)			X																									X	The result must be available prior to first dose of intervention. Perform additional pregnancy tests if a menstrual period is missed, if there is clinical suspicion of pregnancy, or as required by local law or regulation.
Follicle-stimulating hormone (FSH)	X																												Perform as needed to confirm postmenopausal status. Definition in Section 10.4.
C-peptide			X																										
eGFR (CKD-EPI)	X		X													X												X	
Urinary albumin/creatinine ratio (UACR)	X		X													X												X	
Pharmacokinetic (PK) samples			X		X		X									X											X	Visit 3: collect sample at least 15 minutes after dosing. For participants randomly assigned to glargin who are not dosed onsite during Visit 3, the sample may be collected anytime during Visit 3.	

	Screening and Lead-In		Treatment																								Safety Follow-up					
Visit Number	1	2	3	4	5	6	7	8	9	10	11	12	13	14	15	16	17	18	19	20	21	22	23	ED	UV	V801	V802					
Weeks from Randomization	-3	-2	0	1	2	3	4	5	6	7	8	9	10	11	12	14	16	18	20	22	24	25	26	—	—	29	31					
Visit Interval Tolerance (days)		±3	—	±3	±3	±3	±3	±3	±3	±3	±3	±3	±3	±3	±3	±3	±3	±3	±3	±3	±3	±3	±3	—	—	+7	±7					
Visit Detail			F		T	F	T		T	T	T	F	T		T	T		T	T	F	F		T	F	T = telehealth visit; F = fasting visit							

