### **Study participants treated with LY3209590**

Participants will administer their last dose of LY3209590 at Week 25 of the study and can begin the transition to the non-study insulin after Visit 23 (Week 26). At Visit 23 (Week 26), the investigator will review instructions for transitioning to the non-study insulin with the participant. The non-study daily basal insulin treatment should be started slowly and under regular review of glucose profiles after discontinuation of LY3209590.

Since LY3209590 has a half-life of approximately 17 days, a slow up-titration of the non-study daily basal insulin is necessary to prevent hypoglycemia due to overlapping insulin action. Non-study basal insulin would not be required until the study participant's fasting glucose is above 120 mg/dL (6.6 mmol/L), and then daily basal insulin would be initiated and adjusted based on fasting glucose, other SMBGs, hypoglycemia evaluation, and other clinical factors. The investigator should consider titration of the non-study basal insulin to reach 50% of the required daily basal insulin dose at approximately 2 weeks and 80% of the required daily basal insulin dose at approximately 4 weeks. In addition to Visit 801, unscheduled visits may occur during this time to facilitate the transition to non-study daily basal insulin.

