CGM parameters	The baseline will be derived from the data collected during CGM session prior to the first dose date of study treatment.	The CGM sessions prior to Weeks 4, 12, 26 (Visit 7, 15, 23) in EAS2 for MMRM.  The CGM session prior to Week 26 (Visit 23) in EAS1 for ANCOVA with multiple imputation for missing data.
Basal insulin dose	The baseline period is the screening/lead-in period prior to the initiation of study treatment.  The following variables will be derived: 

• daily dose in U

• weekly dose in U

• dose in U/kg/day

 See detailed derivation of variables in Section 4.4.2.1.	All scheduled visits between Week 0 (Visit 3) and Week 26 (Visit 23) in EAS2 for MMRM.  The following variables will be derived: 

• daily dose in U

• weekly dose in U

• dose in U/kg/day

 See detailed derivation of variables in Section 4.4.2.1.

Analysis	Baseline Observations	Post-Baseline Observations
Prandial (bolus) insulin dose	
The baseline period is the screening/lead-in period prior to the initiation of study treatment.
 
The following variables will be derived:
 
 
• daily dose in U
 
• weekly dose in U
 
• dose in U/kg/day
 
 
See detailed derivation of variables in Section 4.4.2.1.
	
All scheduled visits after Week 0 (Visit 3) and up to Week 26 (Visit 23) in EAS2 for MMRM.
 
The following variables will be derived:
 
 
• daily dose in U
 
• weekly dose in U
 
• dose in U/kg/day
 
 
See detailed derivation of variables in Section 4.4.2.1.

Total insulin dose	
The baseline period is the screening/lead-in period prior to the initiation of study treatment.
 
The following variables will be derived:
 
 
• daily dose in U
 
• weekly dose in U
 
• dose in U/kg/day
 
 
See detailed derivation of variables in Section 4.4.2.1.
	
All scheduled visits after Week 0 (Visit 3) and up to Week 26 (Visit 23) in EAS2 for MMRM.
 
The following variables will be derived:
 
 
• daily dose in U
 
• weekly dose in U
 
• dose in U/kg/day
 
 
See detailed derivation of variables in Section 4.4.2.1.

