Basal/total insulin dose ratio	
The baseline period is the screening/lead-in period prior to the initiation of study treatment.
 
See detailed derivation of variables in Section 4.4.2.1.
	
All scheduled visits after Week 0 (Visit 3) and up to Week 26 (Visit 23) in EAS2 for MMRM.
 
See detailed derivation of variables in Section 4.4.2.1.

Fasting glucose by SMBG	
The baseline period is the lead-in period up to the day of first dose of study treatment. Baseline will be derived as the average of all fasting glucose measurements between V2 date and the first dose date.
	
All available data after the day of first dose of study treatment up to Week 26 (Visit 23) in EAS2 for MMRM.
 
Values at each visit will be derived as average of all fasting glucose measurements from the day post prior visit up to the day of the next visit.
 
Data at Week 26 (Visit 23) in EAS1 for ANCOVA with multiple imputation for missing data.

Analysis	Baseline Observations	Post-Baseline Observations
Fasting serum glucose	The baseline is the last non-missing assessment prior to or on the day of the first dose of study treatment.	
All scheduled visits after the day of first dose up to Week 26 (Visit 23) for MMRM
 
Planned measurements at scheduled visits will be included.
 
Data at Week 26 (Visit 23) in EAS1 for ANCOVA with multiple imputation for missing data.

Participant-reported hypoglycemia	The baseline period is the screening/lead-in period prior to the day of first dose of study treatment.	
 
• Treatment period starts on the day of first dose of study treatment and ends 
 
◦ at Week 26 (Visit 23) if completed treatment and Visit 23
 
◦ on the last dose date of study treatment + 10 days for LY3209590, +1 day for glargine if discontinued study treatment early
 
 
 
• Post-treatment period starts from 
 
◦ Week 26 (Visit 23)+1 day if completed treatment and Visit 23
 
◦ last dose date of treatment +11 days for LY3209590, +2 days for glargine if discontinued study treatment early
 
 
 
 
and ends on the last date in the study

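### The SAP's visit-interval rule can leave the Week 26 LY3209590 basal dose empty, because the last dose falls at the preceding visit and no rule says which visit owns a visit-day dose

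*SAP*

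**What the plan says.** Insulin dose at Week 26 (basal, bolus, total, and basal/total ratio) is listed among the other secondary endpoints in Protocol Section 3 and SAP 1.1.

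- **Derivation.** For LY3209590, SAP 4.4.2.1.2 states: "In the LY3209590 group, the average weekly dose of each visit (that is, average of weekly doses since last visit"). For glargine it averages the daily dose over the same between-visit interval and multiplies by 7.
- **Visits modelled.** The basal-dose row of the table in SAP 4.1 reads "All scheduled visits between Week 0 (Visit 3) and Week 26 (Visit 23) in EAS2 for MMRM". The prandial, total and ratio rows begin after Week 0.
- **Last dose.** Protocol 6.6.1: "Participants will administer their last dose of LY3209590 at Week 25 of the study".
- **Propagation.** SAP 4.4.2.1.2: "If either weekly basal insulin dose or weekly prandial insulin dose is missing, the total weekly insulin dose and basal/total insulin dose ratio" are set to missing.
- **Missing values.** SAP 4.4.2.1 leaves them to the MMRM, with compound symmetry for insulin dose. There is no carry-forward. The data cutoff for dose analyses in SAP Section 3 is the earlier of the last study dose and the start of rescue.
- **Day boundary.** None is stated for doses. The one between-visit boundary that SAP 4.1 writes out is for fasting SMBG: "average of all fasting glucose measurements from the day post prior visit up to the day of the next visit".

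**The concern.** Visits are timed from Visit 3. LY3209590 is given at the site at Visits 3 and 4 and then on about the same day each week (Protocol 1.3 and 6.1). Nominal dosing days and nominal visit days therefore coincide, and the last dose lands on the day of Visit 22. Whether the interval from Visit 22 to Visit 23 contains any LY3209590 dose then depends on a boundary that the SAP does not set and on which day within the window Visit 22 took place.

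If the interval is empty, the participant has no Week 26 basal dose, total dose or ratio. If it is empty for everyone in the arm, the LY3209590 mean at Week 26 cannot be estimated from the MMRM. If it is empty for some, the observed values come from participants selected by visit timing, and the model supplies the rest from earlier visits. The Week 25 visit cannot simply stand in for the total and ratio, because Protocol 6.4 schedules prandial recording for the weeks before the visits at Weeks 0–12, 16, 20, 24 and 26, not Week 25.

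**Working it through.** The plan states no figure for missing Week 26 doses, so there is none to reproduce.

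**Inputs**
- Visit calendar (Protocol 1.3, row "Weeks from Randomization"): Visit 21 = Week 24, Visit 22 = Week 25, Visit 23 = Week 26; nominal days 168, 175 and 182.
- Tolerance (Protocol 1.3): ±3 days.
- LY3209590 doses: weekly at Weeks 0 to 25, on days 0, 7, …, 175, which is 26 doses.
- Denominator: 284 LY3209590 completers (SAP Section 5), consistent with 335 × 0.85 = 284.75.

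**Step 1. Everything on schedule**

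| Rule for a visit-day dose | Interval for visit *k* | Dose in Week 25 interval | Dose in Week 26 interval | Empty visit |
|---|---|---|---|---|
| A: belongs to that visit | after Visit *k*−1, up to and including Visit *k* | Week 25 | none | Visit 23 (Week 26) |
| B: belongs to the next visit | from Visit *k*−1, before Visit *k* | Week 24 | Week 25 | Visit 3 (Week 0) |

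Every other treatment visit has at least one dose under either rule. On schedule, Week 26 is missing for 284 of 284 (100%) under A and 0 of 284 under B.

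**Step 2. Which rule the text supports.** Only the basal row of SAP 4.1 includes Week 0, and a Week 0 value exists only under A. The SMBG boundary is also of type A. Neither is a stated rule for doses.

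**Step 3. Visit 22 varies within its window (assumption).** Let Visit 22 fall on day 175 + v, with v from −3 to +3 and the dose on day 175. Visit 23 is no earlier than day 179, so it never precedes the dose.
- Under A the interval is empty if v ≥ 0; under B, if v > 0.
- Uniform v: A = 4/7 = 57.1% (about 162 of 284); B = 3/7 = 42.9% (about 122 of 284).
- Triangular v, weights (4 − |v|)/16: A = (4+3+2+1)/16 = 62.5% (177.5 expected); B = (3+2+1)/16 = 37.5% (106.5 expected).
- If participants always dose on or after the day of Visit 22, B gives 0%.

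**Step 4. Glargine.** Doses are taken daily, but Protocol 6.4 asks for basal dose entry on only one day per week. Visit 22 may be as late as day 178 (175 + 3) and Visit 23 as early as day 179 (182 − 3), so the interval can shrink to one day and may hold no recorded glargine dose. That needs extreme timing; the LY3209590 gap can arise with perfect timing.

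**Step 5. After the fix.** If the Week 25 dose is the Week 26 value, everyone who took and recorded that dose has a Week 26 basal value, so structural missingness is about 0%.

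**The case against.** A reader might infer that the Week 26 insulin dose endpoint is missing for many or most LY3209590 participants while the glargine values are always observed. The documents do not support that.

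- **The boundary is unstated.** The SAP does not exclude a dose taken on the preceding visit day. If it counts, an on-schedule participant has a Week 26 value. The excluding convention is written for SMBG, not for doses. This stands, and it is why the result is a range.
- **The percentages between 0% and 100% are not forecasts.** The documents give only the ±3-day tolerance, not the distribution of Visit 22 or its relation to the dosing day. This stands.
- **Bolus dose at Week 26 is unaffected.** This stands.
- **Glargine is not guaranteed complete,** given the one-day-per-week recording requirement. This stands, though its exposure is much smaller.
- **The boundary may be in the ADaM specifications,** which the SAP Introduction places in separate documents. That is possible, and they are not available here. But a boundary alone does not close the gap: including the preceding visit day empties Week 0, which the basal row lists, and still leaves Week 26 empty when Visit 22 follows the dose.
- **The impact is limited.** These endpoints are outside the multiplicity-adjusted family. Gaps caused by visit timing may well be unrelated to dose, which suits an MMRM. Scheduled titration after Week 12 is at Visits 17, 19 and 21, so the Week 24 and 25 doses are informative about Week 26. This holds for partial missingness. It does not help if the whole arm is empty at Week 26.

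**Conclusion.** The point holds as a derivation gap. The last LY3209590 dose falls nominally on the day of the visit before Week 26, the visit value uses only doses since that visit, and nothing fills an empty interval. Both boundary readings can leave Week 26 empty: 100% on schedule if a visit-day dose belongs to that visit, and 0% on schedule, but not with a late Visit 22, if it belongs to the next. The inclusion of Week 0 in the basal row favours the first reading without settling it.

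The size is 0% to 100% of the LY3209590 arm for basal dose, total dose and ratio. The 57% and 43% figures illustrate an assumed uniform ±3-day spread. The documents do not establish how many participants will in fact be missing, nor a contrast with a fully observed glargine arm. As these are secondary endpoints without multiplicity control, this should be corrected but does not touch the trial's main conclusions.

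**What to change.** In SAP 4.4.2.1.2, assign each LY3209590 weekly dose to the visit that closes its 7-day dosing interval. The Week 25 dose then becomes the Week 26 value. In practice, define this as the most recent weekly dose on or before Visit 23, so that it does not depend on where Visits 22 and 23 fall in their windows, and say what happens if the Week 25 dose was not taken or not recorded. Use the same basal value for the total dose and the ratio. Keep Week 0 as a separately labelled first (loading) dose, so that the basal row of SAP 4.1 remains consistent.

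A Visit 21 to Visit 23 window in both arms would also fill the gap, but it is a different quantity: it averages about two weekly doses and pairs them with prandial data scheduled only for the week before Week 26. The closing-visit rule avoids that mismatch.

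The cost is a change to the derivation text and reprogramming, with no change to dosing or data collection.

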#### **4.4.2.2. Other Safety Endpoints**

The safety measures based on CGM data will be analyzed as described in Section [4.6.2.2.2](#). For other safety measures, the details are provided in Section [4.6](#).

#### **4.4.2.3. Participant Reported Outcomes**

Participant-reported outcome analyses will be based on the EAS2 data.

#### 4.4.2.3.1. *Diabetes Injection Device Experience Questionnaire (DID-EQ) Version 1.0*

##### Description of DID-EQ

The DID-EQ (Matza et al. 2018) is a self-administered, 10-item questionnaire designed to assess participants' perceptions of diabetes injection delivery systems for T2D. Each item is rated on a 4-point scale with higher scores indicating more positive perceptions of the injection device. Items 1 to 7 focus on specific characteristics of diabetes injection device, and these 7 items comprise the Device Characteristics subscale. To compute the Device Characteristics subscale score, the seven individual item scores are first summed, resulting in a subscale raw score and then transformed to a scale of 0 to 100 to obtain a transformed domain score.

The transformed domain score can be calculated by

$$\frac{(\text{sum of raw score} - \text{sum of lowest possible raw score})}{(\text{sum of highest possible raw score} - \text{sum of lowest possible raw score})} \times 100$$

For an example, DID-EQ = ((sum of raw score - 7) / (28-7)) × 100. If answer for the 7 questions (Question 1 to 7) are all 1, then the sum of raw score is 7 and the transformed domain score is 0.

In addition, there are 3 global items:

- Item 8 assessing overall satisfaction
- Item 9 ease of use, and
- Item 10 convenience of diabetes injection devices.

These 3 global items are each scored separately.

Summary statistics for the Device Characteristics subscale will be provided by study treatment. The last non-missing postbaseline measures up to Week 26 (Visit 23) will be analyzed by an ANCOVA model using treatment, strata (country, routine use of personal CGM or FGM at randomization, and baseline HbA1c stratum (<8.0%, ≥8.0%)) as independent variables.

The frequency and proportion of the 3 global items at Week 26 (Visit 23) will be summarized by study treatment. Wilcoxon rank sum test will be used for treatment comparison.

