## 6.3. Measures to Minimize Bias: Randomization and Blinding

### Randomization and stratification

All participants will be centrally randomized and assigned to LY3209590 or insulin glargine using an IWRS. Before the study is initiated, the login information and directions for the IWRS will be provided to each site.

Participants will be randomly assigned in a 1:1 ratio to LY3209590: insulin glargine.

Participants will be stratified based on

- country
- HbA1c stratum (<8% and  $\geq$ 8%) at Visit 1
- Routine use of personal CGM or FGM at randomization (yes/no)

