**1.2. Study Design**

- Study BDCV is a Phase 3, multicenter, randomized, open-label, comparator-controlled study to evaluate the efficacy and safety of once-weekly basal insulin (LY3209590) compared to insulin glargine in participants with T2D who are on once- or twice-daily basal insulin and at least 2 injections per day of prandial insulin prior to entering the study.

- The study includes a 3-week screening/lead-in period, a 26-week treatment period, and a 5-week safety follow-up period.
- Participants will continue prior stable diabetes therapy with 0 to 3 allowed non-insulin antihyperglycemic medications during the study.
- Participants will discontinue their previous basal insulin doses at randomization and will be assigned to either LY3209590 or insulin glargine, and all participants will be treated with prandial insulin, insulin lispro.
- Assignment to treatment groups will be determined by an interactive web-response system (IWRS). Participants will be randomly assigned to 1 of the 2 treatment groups in 1:1 ratio (LY3209590: insulin glargine) at Week 0 (Visit 3). Stratification will be by country, HbA1c stratum at Week -3 (Visit 1) (<8.0%, ≥8.0%), and routine use of personal continuous glucose monitoring (CGM) or flash glucose monitoring (FGM) at randomization.
- This is a treat-to-target study, both treatment groups will undergo titration to achieve an FBG target within the range of 80-120 mg/dL,. The primary endpoint at Week 26 (Visit 23) is based on participants reaching a stable insulin dose in order to achieve glycemic stability approximately 12 weeks in advance of the 26-week primary endpoint. HbA1c is the primary endpoint and reflects glycemic control from the prior 8 to 12 weeks.
- Rescue therapy will be considered during the treatment period if the participants meet the protocol criteria of severe, persistent hyperglycemia.
- If study intervention is permanently discontinued, the participant will be encouraged to continue participation in the study for continued monitoring. Both efficacy (including HbA1c) and safety data will continue to be collected per the schedule of activities in the protocol.

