##### 4.5.3.1. Basal Insulin Experience

###### Likelihood of incorporating into routine

This is a Lilly-developed, participant-completed question to understand the participant's likelihood of incorporating their study insulin into their diabetes management routine. The question is rated on a 5-point scale with responses ranging from "very unlikely" to "very likely."

The frequency and proportion of the last non-missing responses up to Week 26 (Visit 23) will be summarized by study treatment and using Wilcoxon rank sum test for treatment comparison.

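### Five single-item patient-reported outcomes are compared by an unstratified Wilcoxon test although randomization is stratified, which costs a little power if the strata predict the answers

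*SAP*

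**What the plan says.** Randomization has three stratification factors. SAP section 1.2 states: "Stratification will be by country, HbA1c stratum at Week -3 (Visit 1) (<8.0%, ≥8.0%), and routine use of personal continuous glucose monitoring (CGM"). Users of a personal FGM device count with the CGM users in that last factor. Protocol section 6.3 lists the same three, the last as "Routine use of personal CGM or FGM at randomization (yes/no").

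The patient-reported outcomes are then analysed in two ways.

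- **Adjusted for the strata.** The DID-EQ Device Characteristics subscale (SAP 4.4.2.3.1) is "analyzed by an ANCOVA model using treatment, strata (country, routine use of personal CGM or FGM at randomization, and baseline HbA1c stratum". The EQ-5D-5L index and VAS (SAP 4.5.3.2) use an ANCOVA with the same three factors plus the baseline value.
- **Not adjusted.** For the DID-EQ global items on satisfaction, ease of use and convenience, the same section 4.4.2.3.1 gives frequencies and proportions and says "Wilcoxon rank sum test will be used for treatment comparison". The routine-incorporation item (SAP 4.5.3.1) is "summarized by study treatment and using Wilcoxon rank sum test for treatment comparison", and the Preference item is handled identically.

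The global items are ordinal: "Each item is rated on a 4-point scale with higher scores indicating more positive perceptions of the injection device". The two Basal Insulin Experience items have five ordered levels. DID-EQ is an Other Secondary endpoint and the Basal Insulin Experience items are tertiary (SAP 1.1).

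**The concern.** Stratified allocation keeps the arms nearly balanced within each stratum. If strata differ in how people answer, a plain rank sum test still counts that between-stratum variation in its null variance, although the design has largely removed it from the treatment comparison. The test is then conservative, and it is less powerful than one that uses the strata. Differences between countries are plausible, because the questionnaires are self-administered and translated for each region (Protocol 8.1.2), but their size is unknown.

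Two smaller matters follow. Results from one questionnaire would rest on two different adjustments, with no reason given. And for these five items the SAP specifies no treatment-effect estimate or interval, only frequencies and a test.

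**Working it through.** **Nearest stated figure.** No power is given for these items, so the sample size and alpha were checked on HbA1c superiority (SAP section 5: 284 per arm, SD 1.1, difference 0.3, two-sided 0.05).

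- Standard error = 1.1 × √(2/284) = 0.0923, and 0.3/0.0923 = 3.25.
- Power = Φ(3.25 − 1.96) = 90.1%, against the stated 90%.
- 670 × 0.85 = 569.5, consistent with 568 completers.

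**Approximation.** Let R² be the share of response variance explained by the strata, and δ the expected standardized difference of the plain test. With balance within strata, its statistic has variance of about 1 − R² rather than 1:

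- size of the plain test ≈ 2[1 − Φ(1.96/√(1 − R²))]
- power of the plain test ≈ Φ((δ − 1.96)/√(1 − R²))
- power of a stratified test ≈ Φ(δ/√(1 − R²) − 1.96)

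Take δ = 1.96 + 0.84 = 2.80, which is 80% power when R² = 0:

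| R² | Size, plain | Power, plain | Power, stratified |
|---|---|---|---|
| 7% | 0.042 | 80.9% | 82.8% |
| 14% | 0.035 | 81.8% | 85.6% |
| 26% | 0.023 | 83.6% | 90.3% |

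The gains are 1.9, 3.8 and 6.7 points.

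**Simulation.** There were 6,000 trials per cell, each with 568 completers, 1:1 allocation in blocks of 4 within country × CGM/FGM × HbA1c stratum, a four-level item, and plain Wilcoxon set against van Elteren on all three factors. The following are assumptions, not in the documents:

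- 6 or 12 countries, 30% CGM/FGM users, and half the participants in each HbA1c stratum
- category shares of 3/12/45/40%
- a latent shift of 0.26 SD
- strata explaining 0%, 7% (country 5, CGM/FGM 1, HbA1c 1), 14% (10, 2, 2) or 26% (20, 3, 3) of latent variance

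Ranges below are over 6 and 12 countries.

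| Variance explained | Size, plain | Size, stratified | Power, plain | Power, stratified | Gain (points) |
|---|---|---|---|---|---|
| 0% | 0.051–0.053 | 0.051 | 0.776–0.779 | 0.766–0.772 | about −1 to −0.6 |
| 7% | 0.043–0.044 | 0.049–0.050 | 0.776–0.782 | 0.786–0.798 | 1.0 to 1.6 |
| 14% | 0.041–0.043 | 0.055 | 0.781–0.788 | 0.811–0.815 | 2.7 to 3.0 |
| 26% | 0.027–0.030 | 0.048–0.053 | 0.798–0.801 | 0.855–0.857 | 5.6 to 5.7 |

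The Monte Carlo standard error is √(0.05 × 0.95/6000) = 0.003 for size and √(0.78 × 0.22/6000) = 0.005 for power, so 0.055 is within two standard errors of 0.05. The simulated gains follow the approximation and are slightly smaller. The loss is relative to a stratified test; the plain test's own power does not fall as the strata become more predictive. Stratifying by country and CGM/FGM use alone gave power within 0.5 point of the three-factor version.

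One simplification: the simulation treats the randomized HbA1c stratum (Visit 1) and the baseline stratum used in the SAP models as the same. SAP Appendix 1 lists them separately.

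**The case against.** The strongest reply is that nothing here is wrong. A rank test on a single ordinal item is standard and valid. The subscale is a 0 to 100 score suited to ANCOVA, while each global item is scored separately on four points, so different methods within one questionnaire are not a contradiction. The SAP has no general rule that comparisons adjust for strata: Fisher's exact test is a default for categorical measures (SAP 4.1 and 4.6), and the hypoglycemia count models in 4.6.2.2.1 carry no country or CGM/FGM term. Frequencies by arm are reported, so readers can see any difference. All of this stands. It limits the point to an improvement, but it does not explain why the ordinal items of a questionnaire whose subscale is adjusted should not use the same factors.

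Two stronger readings are tempting and should be resisted.

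- A reader might infer that these tests are certain to be conservative. The documents give no figure for how far country, HbA1c stratum or CGM/FGM use predicts the answers, and with no association the size stays at about 0.05.
- A reader might infer a loss of ten points or more. A simulation with a between-country SD of 0.7 residual SD does show 64–65% against 75% for a 0.25 SD shift, but there country alone explains 0.49/1.49 = 33% of latent variance. Nothing in the documents supports so strong an effect.

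**Conclusion.** The point holds as a conditional and minor one. Five items are tested without the stratification factors that the trial randomizes by and that the neighbouring patient-reported analyses include. If those factors predict the answers, the plain test is conservative (size about 0.043 at 7% of latent variance explained, 0.042 at 14%, 0.028 at 26%) and gives up about 1 to 2, 3 and 6 power points respectively. If they do not, nothing is lost. These sizes rest on the assumed number of countries, category shares and effect listed above.

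No false claim can result, because the error is on the conservative side. No stated power is missed, and no multiplicity-controlled conclusion is touched, since SAP 2.1 covers only the primary and key secondary objectives.

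**What to change.** In SAP 4.4.2.3.1 and 4.5.3.1, replace the plain test for all five items with one of these:

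1. A proportional-odds model with treatment, country, routine CGM/FGM use and HbA1c stratum, the same terms as the subscale ANCOVA, reporting the common odds ratio with its 95% CI. This is preferable because it also supplies the missing effect estimate.
2. A van Elteren test stratified by the same factors.

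State which HbA1c stratum (Visit 1 or baseline) is meant, and prespecify how small countries or sparse cells are pooled. The Preference item's not-applicable answer has no rank and must be kept out of the ordinal comparison.

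No new data are needed. The cost is a short SAP edit, the pooling rule, and at most about 1 power point if the strata turn out uninformative. If the plain test is kept, the stratified analysis should at least be added as a prespecified sensitivity analysis.
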